Official title: Validity of an AI-based Program to Identify Foods and Estimate Food Portion Size

NCT number: NCT05343585

Document date: 04/08/2022

Title: Testing the validity of an artificial intelligence-based program to identify foods and estimate food portion size among adults, a pilot study.

Principal Investigator: [name].

Co-Investigator: [name].; [name].; [name].; [name].; [name].

Protocol Version Date: April 4th, 2022

Background:

Accurately quantifying food intake is vital to promoting health and reducing chronic disease risk. Food intake encompasses energy intake, nutrient intake (macronutrients, micronutrients, vitamins, minerals), and intake of various food groups (e.g., fruits, vegetables); thus, it reflects the nutritional status of individuals. Nutrition affects disease risk, including risk of developing obesity,¹ diabetes,² and cancer,³ all of which negatively affect the United States (US). Nonetheless, accurate assessment of food and nutrient intake has remained challenging, despite methodological improvements. Self-report methods, namely food records, are a mainstay of nutritional research,⁴ with food recall being another popular method.⁵ These methods rely on the participant to accurately estimate portion size and, for food recall, remember what was consumed. The accuracy of these methods has been questioned⁶⁻⁹ and the problems with human recall have been comprehensively outlined.¹⁰ As a result, there remains a significant need for methods that are sufficiently accurate to provide users, clinicians, and researchers with data to guide health promotion efforts.

The PortionSize™ app was designed by our laboratory to overcome the limitations outlined above and to guide users to follow specific diets. PortionSize relies on users capturing images of their food selection and waste. Food intake data are immediately provided since the user relies on built-in tools, including templates, to estimate portion size within the app. Although the PortionSize app provides users (and clinicians and researchers) with real-time information about food intake, it comes at the cost of increased user burden since the user must identify foods in their images and estimate portion size. This differs from other food photography-based methods that our laboratory and other groups have developed, including the Remote Food Photography Method© (RFPM) and SmartIntake® app. For example, when using the RFPM and SmartIntake app, users only need to capture images of their foods with the app; identify any foods that are not identifiable from a wrapper, container, or logo; and the app sends the images to the researchers for analysis. Indeed, based on our research, participants view SmartIntake as less burdensome and more preferred compared to PortionSize¹¹, and we expect that this could negatively affect peoples' use of PortionSize over time.

To reduce PortionSize's user burden, we aim to utilize machine learning, image recognition, and artificial intelligence for nutrition tracking. However, before we can incorporate these technologies into PortionSize, they first need to be validated. Therefore, we aim to test the validity of Nutrition AI technology, currently embedded in the Openfit® app, to identify foods and to estimate portion size (food volume) using automated methods. When using the Nutrition AI in Openfit, if the user believes the automated identification of the food and/or portion estimate needs correcting, adjustments can be made manually. However, this user burden is likely to be low and will also be explored in the current study. Therefore, the primary aims of the current pilot study are to: 1a) test the validity of Nutrition AI at

identifying foods, 1b) test the validity of Nutrition AI at quantifying the amount of food provided, and 1c) assess user satisfaction and usability of Nutrition AI in Openfit among adults in Baton Rouge, Louisiana. Openfit is not currently designed to assess plate waste, though Nutrition AI has the potential to assess plate waste and ultimately food intake. Therefore, the secondary aims of this pilot study are to: 2a) test the validity of Nutrition AI to identify plate waste and, 2b) test the validity of Nutrition AI to quantify the amount plate waste, and 2c) to assess user satisfaction and usability of the Nutrition AI in Openfit to assess plate waste, among adults in Baton Rouge, Louisiana. From this data we can calculate food intake (food plated – plate waste).

Primary Hypotheses:

- 1a) Nutrition AI will correctly identify $\geq 70\%$ of foods plated with automated methods, and $\geq 80\%$ after user correction.
- 1b) Compared to weighed values, energy estimates (kcal) of foods plated, from Nutrition AI, will be:
 - i. Within error margins of 20% without user correction (automated)
 - ii. Within error margins of 15% with user correction (semi-automated)

Secondary Hypotheses:

- 2a) Nutrition AI will correctly identify $\geq 60\%$ of plate waste with automated methods, and $\geq 80\%$ after user correction.
- 2b) Compared to weighed values, energy estimates (kcal) of plate waste, from Nutrition AI, will be:
 - i. Within error margins of 20% without user correction (automated)
 - ii. Within error margins of 15% with user correction (semi-automated)

Methods

Study Design

For this pilot study, using a convenience sample, we will recruit up to 25 adults to use the Nutrition AI technology in Openfit to identify and estimate portion size of foods provided and simulated plate waste, and food intake in a laboratory setting at Pennington Biomedical Research Center (PBRC) and/or Louisiana State University (LSU). Laboratory members within the Ingestive Behavioral Laboratory will also test the ability of Nutrition AI to identify foods and to quantify foods provided, plate waste and food intake, in the laboratory. Meals will be simulated, and participants will not consume the foods provided.

Participants and Recruitment

We will recruit up to 25 adults

- Inclusion criteria include:
 - o Male or female, age 18-62 years
 - o Self-reported body mass index (BMI) 18.5-50 kg/m²

- Exclusion criteria include:
 - o Any condition or circumstance that could impede study completion
 - o Unfamiliar with or not able to use an iPhone

NOTE: PBRC and LSU employees (vulnerable populations) will be targeted and invited to participate. The consent form will explicitly specify that if a PBRC or LSU employee chooses not to participate, there will be no impact on their employment.

Procedures

Written informed consent will initially be obtained. We will then obtain:

- Demographics (self-reported): DOB, race, ethnicity, sex, employment, income, marital status, education level (Lifestyle, Demographics, and Health Questionnaire)
- Anthropometrics (self-reported): height, weight, BMI

On being deemed eligible, participants will receive training on how to use the Openfit app housing the Nutrition AI technology. Subsequently, participants will be randomly assigned to one of five study menus (5 participants per menu) of differing calorie levels (see Table 1). Participants will use a provided smartphone to identify foods and quantify the amount of food plated (e.g., an apple) and simulated plate waste (e.g., half an apple) with Nutrition AI. Within each study menu, participants will be served two meals of a similar calorie level. These two meals will be served during the same study visit. To ensure we are testing the validity of the Nutrition AI across differing portion sizes, each meal (e.g., the chicken meal), will be tested across two different study menus where the amount of food provided and plate waste differs. The amount of plate waste will be assigned randomly using an exponential distribution, with the minimal being 0% remaining (i.e., no waste) and the maximum being 74%¹². On average we will aim for ~5% plate waste across tests to reflect average plate waste in free-living conditions¹³.

These tests will be conducted via Openfit in a laboratory-based setting at PBRC or LSU. Simulated food provision and plate waste will be covertly identified and weighed, and participants will not eat the food provided. During the study visit, tasks completed by each participant on the iPhone will be recorded using the record function on the iPhone and the recording will be saved to the iPhone camera roll. Data will be accessed from the iPhone at study completion. Consent, training, and testing will span up to ~2 hours.

Near the end of the visit, participants will complete the Computer System Usability Questionnaire (CSUQ) ¹⁴. The CSUQ is a standardized, reliable, and valid questionnaire originally designed to evaluate computer programs that has been used to quantify the usability of mobile phone apps. Participants will also complete a user satisfaction survey to quantify satisfaction and ease of use of Openfit for tracking dietary intake.

Outcome measures

Primary outcomes:

1a) Agreement surrounding identification of food and beverages provided compared with known identification, at the item level (e.g., for burger n=10), and across all items where identification is determined by:

- I. Nutrition AI without user correction (automated)
- II. Nutrition AI with user correction (semi-automated)

1b) Error between mean estimates of portion weights (g), energy (kcal) and macronutrients (fat, carbohydrates, protein) and known portion weights, energy, and macronutrients of provided food and beverages, where estimates are determined by:

- I. Nutrition AI without user correction (automated)
- II. Nutrition AI with user correction (semi-automated)

1c) User satisfaction and usability of Nutrition AI for identification of food and beverages and for estimating portion size.

Secondary outcomes:

2a) Agreement surrounding identification of plate waste compared with known identification, at the item level (e.g., for burger n=10), and across all items, where identification is determined by:

- I. Nutrition AI without user correction (automated)
- II. Nutrition AI with user correction (semi-automated)

2b) Error between mean estimates of portion weights (g), energy (kcal) and macronutrients (fat, carbohydrates, protein) and known portion weights, energy, and macronutrients of plate waste, where estimates are determined by:

- I. Nutrition AI without user correction (automated)
- II. Nutrition AI with user correction (semi-automated)

2c) User satisfaction and usability of Nutrition AI for identification of food and beverages and for estimating portion size of plate waste.

2d) Error between mean estimates of portion weights (g), energy (kcal) and macronutrients (fat, carbohydrates, protein) and known portion weights, energy, and macronutrients of food intake (food plated – plate waste), where estimates are determined by:

- I. Nutrition AI without user correction (automated)
- II. Nutrition AI with user correction (semi-automated)

Statistical analyses

For a food identified through the Nutrition AI to be considered an exact food match, the name of the food identified must match or be a close match to the food served. For example, a fruit cocktail identified as a fruit salad is an acceptable match¹⁵. Proportions will be used to assess whether the percentage of food items plated that were correctly identified by Nutrition AI is different to the percentage of foods correctly identified by a criterion method (human rater). Descriptive data will also be used to describe the frequency at which food plated and plate waste were correctly identified.

Mean error and Bland-Altman analysis¹⁶ will be performed to determine errors in estimation of energy intake and food group servings from the Nutrition AI compared to estimations from the criterion measure¹⁷.

Responses to the user satisfaction and usability questionnaires will be assessed using frequencies and percentages for Likert scale data. Open responses will be evaluated using qualitative methods to identify common themes.

Provisions to Monitor the Data to Ensure the Safety of Subjects

Adverse events will be monitored.

Withdrawal of Subjects

Subjects may be withdrawn from the study at any time. If a subject voluntarily withdraws from the study, no additional data will be collected, and they will be considered dropouts in the study.

Risks to Subjects

This study involves no greater than minimal risk. The main risk is breach of confidentiality, and the PBRC team will work to minimize this during data collection, handling, and analysis.

Potential Benefits to Subjects

Participants may benefit by increased awareness of energy and nutrients in food served.

Sharing of Results with Subjects

Participants will have access to the study results once published.

Setting

The Ingestive Behavior, Weight Management, and Health Promotion Laboratory at PBRC, and [name] or [name] at LSU.

Compensation

Participants will receive \$50 for the successful completion of the study.

Provisions to Protect the Privacy Interests of Subjects

All attempts will be made to maintain a subject's privacy. Safeguards such as password protected computers and networks have been put in place to limit access to subject data. Subjects will be given ample time to read over the consent, ask questions, and agree to participate in the research study. Subjects may decline to answer questions with which they are not comfortable. Each procedure will be explained to the subject before it is performed. We will always ensure the privacy of the subjects.

Compensation for Research-Related Injury

No compensation will be provided for research-related injury.

Economic Burden to Subjects

All study-related tests and procedures will be at no cost to the subject.

Consent Process

A designated and trained staff member will obtain informed consent during the visit. Ample opportunity will be given for the subject to review the consent form and ask any questions prior to signing the form. If subjects wish, they can take the form home and return at a different visit. We are aware that consent is an ongoing process.

Table 1. PortionSize AI Groups

Menu 1- 400 kcal each meal	
Burger Tomato Onion Burger bun Cheese slice Ketchup Cookies Coke	Chicken Ready Rice Oranges Carrots Butter Sweet Tea
Menu 2- 800 kcal each meal	
Chicken Ready Rice Oranges Carrots Butter Sweet Tea	Pizza Lettuce Tomato Dressing Cookies Coke
Menu 3- 500 kcal each meal	
Pizza Lettuce Tomato Dressing Cookies Coke	Pork Chop Broccoli Butter Apple Slices Sweet Tea
Menu 4- 700 kcal each meal	
Pork Chop Broccoli Butter Apple Slices Sweet Tea	Lettuce Carrot Tomato Pre-cooked frozen chicken Dressing Milk
Menu 5- 600 kcal each meal	
Lettuce Carrot Tomato Pre-cooked frozen chicken Dressing Milk	Burger Tomato Onion Burger bun Cheese slice Ketchup Cookies Coke

References

4. Willett WC. *Nutritional epidemiology*. New York: Oxford University Press; 1998.

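### Each meal is randomised at two portion sizes to test validity across portion sizes, but no analysis of estimation error by portion level, meal or menu is specified

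*Combined protocol and SAP*

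**What the plan says.** All places are in the combined protocol and SAP.

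- **Methods, Procedures.** Within the plan to recruit ("we will recruit up to 25 adults"), "participants will be randomly assigned to one of five study menus (5 participants per menu) of differing calorie levels". Within a menu, "participants will be served two meals of a similar calorie level". The purpose is stated ("To ensure we are testing the validity of the Nutrition AI across differing portion sizes"), and so is the device: each meal "will be tested across two different study menus where the amount of food provided and plate waste differs".
- **Table 1.** Five calorie levels, one per menu, for example "Menu 2- 800 kcal each meal". The resulting pairs are burger 400/600, chicken 400/800, pizza 500/800, pork 500/700 and salad 600/700 kcal.
- **Primary Hypotheses, 1b.** Energy estimates of plated food are to fall within 20% (automated) and 15% (semi-automated) of weighed values.
- **Outcome measures, 1b.** The outcome is the error between mean estimates and known values. Identification (1a) is reported by item and overall; the item example, burger n=10, combines both portion sizes.
- **Statistical analyses.** Mean error and a Bland-Altman analysis "will be performed to determine errors in estimation of energy intake and food group servings from the Nutrition AI". No menu, meal, portion level, trend or slope is named, and neither the Bland-Altman axis nor the two meals per participant is mentioned.

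**The concern.** The one structured feature of the design is the pairing of each meal at two sizes, and the protocol gives portion size as the reason for it. Nothing in the analysis section says how that pairing will be read.

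This is more than missing detail. Each meal occurs equally often at its smaller and larger size, so overestimation of small portions can cancel underestimation of large ones. A tool that responds weakly to the amount on the plate could then meet both margins on mean error. The report could state validity for quantifying plated food without showing that the estimate follows the amount served.

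**Working it through.** **Inputs.** Menus, meals and kcal are from Table 1; five participants per menu and two meals each are from Procedures; the 20% and 15% margins are from Primary Hypotheses. Table 1 kcal is taken as the weighed value. The documents give no SD of the estimation error and no within-participant correlation (ICC). I assume SD 120 to 180 kcal and ICC 0 to 0.5.

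**1. The plan's own counts.** 5 menus × 5 = 25 participants and 50 meals. Burger is in menus 1 and 5, so 2 × 5 = 10. Both match the documents. The 10 is 5 at 400 kcal plus 5 at 600 kcal.

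**2. Half-response tool.** Let estimate = meal average + 0.5 × (kcal − meal average). The meal averages are burger 500, chicken 600, pizza 650, pork 600 and salad 650.

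| Meal | Smaller size | Larger size |
|---|---|---|
| Chicken | 400: +100/400 = +25% | 800: −100/800 = −12.5% |
| Pizza | 500: +75/500 = +15% | 800: −75/800 = −9.4% |
| Burger | 400: +50/400 = +12.5% | 600: −50/600 = −8.3% |
| Pork | 500: +50/500 = +10% | 700: −50/700 = −7.1% |
| Salad | 600: +25/600 = +4.2% | 700: −25/700 = −3.6% |

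The kcal errors sum to zero, so pooled error is 0%; the mean of the ten percentages is +2.6%. Nine of ten are within 20%, and only one exceeds 15%.

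**3. Tool that ignores portion size within a meal.** Every error in the table doubles. Pooled error is still 0% (mean of percentages +5.1%), with chicken at +200/400 = +50% and −200/800 = −25%.

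**4. What Bland-Altman would show for the half-response tool.** Over the ten menu-meals, total SS of kcal about 600 is 200,000, of which 170,000 (85%) is within meal and 30,000 between meals.
- *Weighed kcal on the x-axis:* slope of error = −0.5 × 170,000/200,000 = −0.425, against −0.50 within meal. Most of the trend is visible.
- *Mean of the two methods on the x-axis:* slope = [(Var E − Var K)/2] / [(Var E + Var K + 2 Cov)/4], where E is estimated and K is weighed kcal. Var K = 200,000/10 = 20,000. Var E = (30,000 + 0.25 × 170,000)/10 + 120² = 7,250 + 14,400 = 21,650. Cov = (30,000 + 0.5 × 170,000)/10 = 11,500. Slope = 825/16,162.5 = 0.05; simulating 50 meals gives about 0.03. The trend disappears.
- *Meal-specific bias:* add −100 kcal to burger and +50 kcal each to pizza and salad. Pooled error stays 0, but the weighed-axis slope moves by (−100 × −200 + 50 × 100 + 50 × 100)/200,000 = +0.15, from −0.425 to −0.275. The within-meal response has not changed. A meal-type factor removes this distortion.

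**5. Precision of a within-meal slope.** With five participants per menu, within-meal SS is 850,000. At ICC 0, SE = 120/√850,000 = 0.130; generalised least squares gives 0.144 at ICC 0.3 and 0.152 at ICC 0.5. The 95% half-width is 1.96 × SE, about 0.26 to 0.30. At SD 180 the SE is 0.20 to 0.23, and the half-width about 0.38 to 0.45.

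**6. Precision elsewhere.** Within one meal the size contrast is 5 against 5; at two-sided 5% and 80% power only about 2.02 SD is detectable. At one calorie level there are ten meals from five people, so the 95% half-width of mean error lies between 0.72 SD (meals independent) and 1.24 SD (pairs fully correlated).

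**7. Why both summaries are needed.** A constant +100 kcal bias has slope exactly 1 and pooled error 100/600 = 16.7%, yet is 25% at 400 kcal and 12.5% at 800 kcal; only the by-level errors show this. Conversely, the half-response tool averages (25 + 12.5)/2 = 18.75% at 400 kcal, inside 20%; the slope of 0.5 shows its fault plainly.

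**The case against.** The stated purpose can be read as coverage: the two-menu scheme keeps the sample from sitting at one serving size, and the data do span 400 to 800 kcal. No within-meal comparison is promised, and hypotheses 1b concern overall margins. On this reading nothing promised is missing. That stands in part. A reader might infer that the portion-size purpose will never be carried out; the documents support only that its analysis is not specified.

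A reader might also infer a commitment to one pooled analysis. The section is silent on grouping, the outcomes separate the two modes and separate plated food, waste and intake, and identification is reported by item. The plan is under-specified rather than committed to pooling.

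Nor is Bland-Altman blind to portion size whatever its axis. Against weighed kcal it recovers −0.425 of −0.50. But neither that axis nor a slope is stated, and the section names intake and food group servings rather than amount plated.

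The zero pooled error is a special case. It needs shrinkage toward a target that averages the study mean of 600 kcal. Half-shrinkage toward 500 kcal gives 0.5 × (500 − 600)/600 = −8.3%, and toward 450 kcal −12.5%. Both still meet the 15% margin.

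Finally, this is a convenience-sample pilot with descriptive analyses, and the SDs are assumed. That argues for estimation and modest weight, not for leaving the contrast unread.

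**Conclusion.** The point holds as an omission in the analysis plan. The portion contrast is randomised for a stated reason, and no analysis of estimation error by portion level, meal or menu is specified. Mean error can be 0% for a tool with errors of +25% and −12.5%, or +50% and −25%, on the same meal at its two sizes. Those chicken figures are the extremes of Table 1; for the half-response tool most menu-meals are much closer.

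These examples depend only on Table 1 and the assumed tool behaviour. They show what mean error can miss, not how Nutrition AI performs. The mean-of-methods result and the slope precision rest on the assumed SD and ICC, and on one common slope across meals with all 25 participants recruited. It would be too strong to infer that the data will settle the question: at SD 180 the interval on the slope is about ±0.38 to ±0.45. For a pilot this is a change that should be made, but it does not undermine the study.

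**What to change.** Add to Statistical analyses, for food plated and separately for the automated and semi-automated modes:

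- (a) Mean percentage error with 95% CI at each of the five calorie levels, with intervals that allow for two meals per participant.
- (b) The slope, with 95% CI, from a regression of AI-estimated on weighed kcal, and likewise grams, with meal type as a fixed factor and a participant random intercept. A slope of 1 means the estimate follows portion size; 0 means it does not.
- (c) Weighed values as the x-axis of any Bland-Altman trend.

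Present these as estimates, not tests. Rest any statement of validity across portion sizes on the slope and the by-level errors together.

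The cost is a few sentences, one table, and one model per mode and measure, with no new data or participants. The result may be less favourable than the pooled error.

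### The one comparison planned for food identification sets the AI against an undefined human rater, not against the 70% and 80% targets of hypothesis 1a, and the frequency that could be read against them has no interval.

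*Combined protocol and SAP*

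**What the plan says.** Primary Hypotheses, 1a, states two absolute targets: at least 70% "of foods plated with automated methods" and at least 80% after user correction. Secondary Hypotheses, 2a, states at least 60% "of plate waste with automated methods" and at least 80% after correction.

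Outcome measures 1a and 2a define agreement against known identification, for single items and over all items, with automated and semi-automated use kept apart. Procedures supplies that reference: "Simulated food provision and plate waste will be covertly identified and weighed".

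Statistical analyses has three statements on identification:

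- The match rule: "the name of the food identified must match or be a close match to the food served".
- The comparison: proportions are used to assess whether the AI's percentage correct for plated items "is different to the percentage of foods correctly identified by a criterion method (human rater").
- The description: "Descriptive data will also be used to describe the frequency at which food plated and plate waste were correctly identified".

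The section does not mention 60%, 70% or 80%, and plans no confidence interval for identification. The mean-error and Bland-Altman sentence concerns energy and food group servings, so it does not bear on identification.

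**The concern.** A target of 70% or 80% is a statement about the AI's own accuracy against the truth. A difference from a human rater is a statement about two accuracies. The second does not settle the first: an AI at 75% and an AI at 65% can both differ clearly from a good rater, although one meets the automated target and the other misses it.

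The figure that does bear on the target is the descriptive frequency, and it is planned as a bare percentage. Each participant contributes several items in one visit, using the same phone and technique, so errors may run together within a person. The Background says the technology has to be validated before it is built into PortionSize, and 1a is the first of the primary hypotheses. Readers of the result will want to know how firmly a target was met or missed, and the plan as written does not tell them.

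**Working it through.** **The plan's own figure.** Procedures puts 5 participants on each of 5 menus, so 5 x 5 = 25. Each meal appears in two menus, so 5 x 2 = 10 servings per meal. This matches the n=10 given for the burger in Outcome measures.

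**Item count.** From Table 1, counting every listed component: burger meal 8, chicken 6, pizza 6, pork 5, chicken salad 6, total 31. Then 31 x 10 = 310 plated items. Menus 1 to 5 give 14, 12, 11, 11 and 14 items per participant.

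**Allowance for clustering.** The size-weighted mean number of items per participant is

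m = (14² + 12² + 11² + 11² + 14²) / (14 + 12 + 11 + 11 + 14) = 778 / 62 = 12.55.

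Design effect = 1 + (m - 1) x ICC, where ICC is the within-participant intraclass correlation. Effective n = 310 / design effect. The documents give no ICC, so 0, 0.05 and 0.3 are assumptions that show a range.

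- ICC 0.05: 1 + 11.55 x 0.05 = 1.58; effective n = 196.5.
- ICC 0.3: 1 + 11.55 x 0.3 = 4.46; effective n = 69.4.

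**Exact (Clopper-Pearson) 95% intervals on the effective n:**

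| Assumed ICC | Effective n | Observed 70% | Observed 80% |
|---|---|---|---|
| 0 | 310 | 64.6-75.0% | 75.1-84.3% |
| 0.05 | 196.5 | 63.1-76.3% | 73.7-85.4% |
| 0.3 | 69.4 | 57.8-80.4% | 68.7-88.6% |

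**Sensitivity to the scoring unit.** If the burger with its components, the side salad and the chicken salad each count as one item, the meals have 3 + 6 + 4 + 5 + 2 = 20 items, so 200 in all. Participants then have 9, 10, 9, 7 or 5 items, with m = 336 / 40 = 8.4. At ICC 0.3 the design effect is 1 + 7.4 x 0.3 = 3.22 and the effective n is 62.1. An observed 70% has 63.1-76.3% with independent items and 57.0-81.0% at ICC 0.3; an observed 80% has 73.8-85.3% and 67.9-89.1%. The picture is much the same.

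**What the rater comparison can show.** Suppose the rater is a fallible person who is 95% correct (an assumption). With 310 items per method treated as independent, a two-sided 5% test of difference finds one with probability about 1.00 whether the AI's true rate is 65% or 75%. With a 90% rater the probabilities are about 1.00 and 0.999. These ignore pairing and clustering and are only illustrative. Suppose instead that the rater is the record of what was served. The rater is then correct by definition, and the contrast is AI against 100%. In neither case is the AI compared with 70% or 80%.

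**The case against.** The best reply is that the estimate is already there. The rater is called a criterion method, and the served items are identified covertly, so the rater may simply be the record of what was served. A comparison with 100% then shows the AI's percentage correct, which is the quantity 1a names. The descriptive sentence gives the same figure for plated food and plate waste, Outcome measures already fixes the reference and the automated/corrected split, and the shared label 1a lets a reader trace the target. This is also a pilot with a convenience sample of up to 25, and intervals can be added at reporting. Most of this stands. It leaves the missing interval, the missing allowance for clustering and the missing statement that the percentage is to be read against the target.

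A reader might infer more than the documents support:

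- That hypothesis 1a has no analysis at all. The descriptive frequency supplies its point estimate.
- That the plan will run a significance test and declare almost any AI result different. Under an exact paired two-sided 5% test against a rater who is always right, six errors in 310 would suffice (p = 2 x 0.5^6 = 0.031). But the plan names no test and no significance level, and the sentence may be purely descriptive.
- That the rater problem extends to plate waste. The rater sentence covers plated items only; for 2a the gap is the interval and the link to 60% and 80%.
- That the interval must also cover variation between foods. That would answer whether the result carries over to other foods, whereas 1a speaks of the foods plated.

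**Conclusion.** The concern holds for 1a in this form: the one stated identification comparison does not show whether a target is met, and the frequency that could show it has no measure of uncertainty and no stated link to the targets. For 2a only the second part applies.

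On 310 items the 95% limits lie about 4 to 5 points from the observed percentage with independent items, and about 9 to 12 points from it at a within-participant correlation of 0.3. This rests on full recruitment of 25, every Table 1 component scored separately and assumed correlations. The true width could lie anywhere in or outside that range. The lack of a formal test or a power calculation is not held against a pilot of this kind. This is a cheap improvement worth making before the data are seen, not a flaw that undermines the study.

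**What to change.** In Statistical analyses, add wording such as:

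> With the known identity of the served item as reference, the percentage of plated items correctly identified across all items will be reported separately for automated and semi-automated identification, with a 95% confidence interval that allows for clustering of items within participant, and read against 70% and 80% (hypothesis 1a). Plate waste will be reported in the same way against 60% and 80% (hypothesis 2a). Any comparison with a human rater is supportive and paired by item.

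Also define the human rater: who it is, what the rater sees, and whether this is the same as the record of what was served.

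The cost is one paragraph. No new data are needed, because the served items are already identified, and no formal test need be added. The downside is that the intervals will be fairly wide with up to 25 participants, so a result near a target may have to be reported as inconclusive.
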